An intervention is considered efficacious if significant benefit is shown for either of the two primary endpoints (FEV₁, or asthma symptom control score). Because there are multiple chances for an intervention to demonstrate efficacy, multiplicity adjustments are required. We will use the Hochberg method to adjust for multiplicity. According to the Hochberg method, the treatment is declared effective if the treatment-placebo comparison is significant at level α for both outcomes or it is significant at $\alpha/2$ for at least one of the outcomes.

A sample size of 111 participants for each intervention is required to achieve at least 80% power to detect a treatment effect with respect to at least one of the two primary endpoints equal to 0.3 times the standard deviation (SD) of that outcome, taking into account the possibility of stopping for futility with a non-binding stopping rule. If participant accrual in the target subgroup of one or more interventions is such that an interim futility analysis is not possible or practical (e.g., the study will conclude before the recommendations of the interim futility analysis can be implemented), the interim analysis will not be performed. In this case, 93 participants (2:1 ratio of biomarker positive to negative participants) are required to provide similar power for the final analysis.

All participants randomized to an active intervention or matching placebo will be included in the final efficacy analysis, but only participants who do not withdraw from the study prior to the start of period 2 are counted towards the required total sample size in estimating power. We also assume that about 10% of participants will discontinue an active treatment period soon after randomization in the power calculations. Attrition is monitored throughout the study, and the required sample size may be adjusted, if the treatment discontinuation rate is different from 10% or discontinuations occur later in the treatment period. This adjustment, if needed, will take place prior to any unmasking of treatment assignments, that is, prior to the interim futility analysis or, if the futility analysis is not feasible for an intervention, prior to the final analysis.

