The Type I error probability will be controlled under the global null hypothesis (no effect on either endpoint) at $\alpha \leq 0.10$ two-sided. Power was estimated under the assumption of a within-participant, between-period correlation of responses in consecutive placebo and test treatment periods of 0.70.

Examples of treatment effects yielding a 0.3 standardized effect size include: a difference of 4.3 percent predicted FEV₁ between intervention and placebo with a SD of 14.5 percent predicted; and a difference of 0.18 in average ACQ-6 symptom scores between the intervention and placebo with a SD of 0.6.

Our analysis method ensures strong control of the Type I error probability at $\alpha = 0.10$ two-sided for each intervention. This value was chosen to reflect the experimental nature of this phase 2 proof-of-concept study. Taking into account both our stopping rule for futility and the Hochberg method for controlling multiplicity due to multiple primary endpoints, the Type I error probability is expected to equal about 0.05. Interventions that demonstrate evidence of efficacy in PrecISE with respect to at least one of the two primary endpoints may be studied further in a more fully powered phase 3 trial to provide substantial evidence of efficacy, controlling the Type I error probability at the more usual level of 0.05. Information learned from PrecISE regarding the optimal target subgroup for the intervention should be useful in developing an enrichment strategy for such a study.

No adjustment for multiplicity with respect to the multiple interventions in the study is planned. Success is defined independently for each intervention, and interventions will not be compared to each other in the efficacy analyses.

We are planning to enroll 395 participants. Assuming a study withdrawal rate of 2% a month, we anticipate that each participant will contribute data to two active interventions on average. This will allow us to accumulate required number of active treatment periods to test efficacy in all five interventions.

6. Data Sources, Documentation, and Verification of Results

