7.4 Analysis of Primary Efficacy Endpoints

7.4.1 Statistical Model

The final analysis to assess the efficacy of an intervention will be performed when accrual and follow-up for that intervention are complete and will include biomarker positive and biomarker negative participants randomized to the intervention unless the biomarker negative subgroup is dropped after the interim futility analysis, i.e., cavosonstat. In this case, the primary analysis will include only biomarker positive participants assigned to that intervention. Data from the treatment period in which a participant was randomized to the intervention plus the matched placebo period associated with that participant are included in the final analysis of the intervention. If there is no matched placebo, all placebo periods obtained on that participant are included.

Treatment effects with respect to each of the two primary endpoints (FEV₁ and ACQ-6) will be estimated using a mixed model for repeated measurements (MMRM) that appropriately takes into account the within-participant correlations between periods. The MMRM will include treatment (test vs placebo), time (visit nested within period), subgroup levels and baseline values (FEV₁ and ACQ-6), measured before the first randomization, as fixed effects. The model will also include two-way interactions (fixed effects) between treatment and time and baseline and time. Subgroup-specific treatment effects will be estimated by including subgroup by treatment interaction. Unstructured variance-covariance matrix will be used to model covariances within each treatment period. If the model does not converge with an unstructured variance-covariance matrix, the Toeplitz variance-covariance matrix will be used. The model will include a subject-level random intercept to model between-period correlation. If the model fails to converge, other variance-covariance structures will be evaluated until model convergence is achieved. If the variance-covariance matrix in MMRM cannot be estimated well, we will include more data on the participants in the analysis population for that intervention.

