For a given intervention and outcome let T_k^* be the test statistic for the treatment effect in biomarker positive participants and T_k^{All} be the test statistic in all participants computed using stage k , $k = 1, 2$, data. The tests are from the corresponding MMRM (subscripts indicating intervention and outcome are omitted here). In the final analysis, the treatment effect of a given intervention with respect to that outcome is performed using the inverse normal combination approach by computing the p-value: $p = 1 - \Phi(\sqrt{0.45} \Phi^{-1}(1 - p_1) + \sqrt{0.55} \Phi^{-1}(1 - p_2))$. Here p_1 and p_2 are the stage 1 and stage 2 p-values. The first stage p-value, p_1 , is computed based on the test statistic $\max(T_1^*, T_1^{All})$ using the skew normal distribution with parameters $(0, 1, .32)^6$ as a reference distribution. If the biomarker negative subgroup is not dropped at the interim analysis, the second stage p-value is computed similarly to the stage 1 p-value. If the biomarker negative subgroup is dropped at the interim analysis, the second stage p-value, p_2 , is computed based on the test statistic T_2^* using the standard normal distribution as a reference distribution. The weights $\sqrt{0.45}$ and $\sqrt{0.55}$ in the inverse normal formula correspond to a futility analysis performed at the 0.45 information fraction. If futility is performed at an information fraction xt , the weights \sqrt{x} and $\sqrt{1-x}$ will be used. For interventions without an interim analysis, the final analysis for a given outcome is performed as follows. Five possible cutoffs b_1, b_2, b_3, b_4, b_5 are identified for the primary continuous biomarker that defines the biomarker positive subgroup for that intervention. The five potential subgroups are defined as participants with the biomarker values $\geq b_i$ if the treatment effect is assumed to be increasing with the biomarker values, and $\leq b_i$ otherwise. The test statistic $\max(T^1, T^2, T^3, T^4, T^5, T^{All})$ is compared with 2.163 for a 0.05 one-sided level and with 2.452 for a 0.025 one-sided

level. These critical values were computed based on the joint distribution of the six test statistics under the null hypothesis and assuming that the cutoffs represent the quantiles of the biomarker distribution.⁷

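### On the no-interim route, the critical values 2.163 and 2.452 treat variances as known, so the one-sided error rate is slightly above 0.05, and higher still if each subgroup is fitted separately.

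*SAP*

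**What the plan says.** SAP 7.4.1 gives a separate primary test for interventions that have no interim. "Five possible cutoffs b_1, b_2, b_3, b_4, b_5 are identified for the primary continuous biomarker", and these define five nested subgroups. The test statistic is the largest of the five subgroup statistics and the all-participant statistic, and it "is compared with 2.163 for a 0.05 one-sided level and with 2.452 for a 0.025 one-sided" level. On the origin of these values the SAP says: "These critical values were computed based on the joint distribution of the six test statistics under the null hypothesis", "assuming that the cutoffs represent the quantiles of the biomarker distribution". It does not give the quantile levels.

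On the origin of the statistics, the section says "The tests are from the corresponding MMRM". The paragraph before it, which specifies the model, says "Subgroup-specific treatment effects will be estimated by including subgroup by treatment interaction". Neither paragraph names a degrees-of-freedom method, a t reference or any other small-sample adjustment.

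SAP Section 5 sets the size for this route: "In this case, 93 participants (2:1 ratio of biomarker positive to negative participants) are required to provide similar power for the final analysis". It assumes about 10% early discontinuation of active treatment and uses Hochberg across FEV1 and ACQ-6. On the overall level, 0.10 two-sided for each intervention, it states: "Our analysis method ensures strong control of the Type I error probability".

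**The concern.** A critical value from a joint normal distribution is exact only when the standard errors are known. Here they are estimated, so each statistic has heavier tails than a normal. Taking the maximum over nested subgroups favours the statistic with the heaviest tail. If each subgroup supplies its own variance estimate, that is the smallest subgroup.

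This rule is the primary efficacy decision for any intervention that reaches it. SAP Section 5 expects the actual error to be about 0.05 once futility stopping is counted. That margin is not available here, because nothing can be stopped at an interim that does not take place. False wins that come from small subgroups would also misdirect the enrichment of later trials, which the SAP names as a use of the results.

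**Working it through.** **Inputs from the documents.** Cut-offs 2.163 and 2.452, and six statistics (SAP 7.4.1). 93 participants, 10% discontinuation, Hochberg, and between-period correlation 0.70 (SAP Section 5).

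**Assumptions.** Sextile cutoffs, inferred because they reproduce the SAP's values. Normal outcomes, complete treatment–placebo pairs unless stated, and discontinuers contributing nothing. In the multi-visit model, within-period residual correlation 0.5.

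**Step 1: reproduce the plan's figures.** With sextile cutoffs the subgroups hold 1/6, 2/6, …, 6/6 of the sample, and corr(T_i, T_j) = √(n_i/n_j) for n_i ≤ n_j. With known variances the maximum is that of S_i/√i for i = 1 to 6, where S_i is the sum of i independent standard normals. In 4 million draws its 95% and 97.5% points are 2.1625 and 2.4514. Other layouts fit less well: cutoffs at 10/25/50/75/90% give 2.188 and 2.473. The SAP's values are therefore normal, known-variance values.

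**Step 2: subgroup sizes.** 93 × 0.9 = 83.7, about 84 contributors. The smallest subgroup is 93 × 0.9 / 6 = 13.95, about 14. With no discontinuation it is 93/6 = 15.5.

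**Step 3: why the model behind each T matters.** For a paired comparison, a separate fit to 14 people has 14 − 1 = 13 degrees of freedom. A whole-sample fit with two subgroup effects has 84 − 2 = 82. For the smallest subgroup alone, the probability of exceeding 2.452 is 0.0071 for a normal, 0.0082 for t with 82 df and 0.0146 for t with 13 df.

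**Step 4: error rates under the null, 84 contributors.** Hochberg succeeds if either maximum exceeds 2.452 or both exceed 2.163. With per-endpoint rates a (at 2.163) and b (at 2.452) and independent endpoints, the rate is 1 − (1 − b)² + (a − b)². At nominal values this is 1 − 0.975² + 0.025² = 0.050.

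| Source of T and simulation | a (0.05) | b (0.025) | Hochberg (0.05) |
|---|---|---|---|
| Interaction model, paired differences, endpoints independent | 0.0543 | 0.0283 | 0.0571 |
| Same, endpoint correlation 0.5 | 0.0544 | 0.0284 | 0.0543 |
| Interaction model, 4-visit REML MMRM | 0.0558 | 0.0297 | 0.0591 |
| Separate fits, paired differences, endpoints independent | 0.0643 | 0.0364 | 0.0715 |
| Same, endpoint correlation 0.5 | 0.0635 | 0.0359 | 0.0674 |
| Separate fits, 4-visit REML MMRM | 0.0646 | 0.0385 | 0.0763 |

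Paired-difference rows use 300,000 replicates. MMRM rows use 12,376 (standard error of a about 0.002) and independent endpoints. Putting the unrounded rates into the formula: for interaction, 1 − (1 − 0.02965)² + (0.05583 − 0.02965)² = 0.0591; for separate fits, 1 − (1 − 0.03854)² + (0.06456 − 0.03854)² = 0.0763.

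**Step 5: sensitivity.** With 93 contributors the paired interaction model gives 0.054 per endpoint and 0.054 to 0.056 with Hochberg. Separate fits give 0.062 to 0.063 and 0.066 to 0.070. Across all the simulations of the interaction model the Hochberg rate runs from 0.052 to 0.059. With separate fits and half of the participants lacking a matched placebo, an end-of-period REML model gives 0.071 to 0.072 per endpoint and 0.079 to 0.083 with Hochberg. The documents give no figure for the unmatched share.

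**Step 6: after correction.** Each T is replaced by z = Φ⁻¹(1 − p), where p is its one-sided t p-value. With paired differences, the rates at 2.163 and 2.452 become 0.0505 and 0.0249 (interaction) and 0.0506 and 0.0254 (separate fits). Without conversion, the cut-offs needed at 84 contributors would be about 2.21 and 2.50 (interaction) or 2.28 and 2.62 (separate fits).

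**The case against.** The strongest reply is that the only model SAP 7.4.1 describes pools the variance. Subgroup level is a fixed effect, and subgroup effects come from an interaction with treatment, so the standard error for the smallest subgroup rests on all contributors. Separate fits are not described anywhere. On that reading the excess is below 0.01, in a proof-of-concept trial that deliberately chose 0.10 two-sided. This stands, and it sets the severity.

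A reader might infer that the true family-wise rate is simply 0.07 to 0.08. The documents do not support that as a flat statement. It requires every subgroup to be fitted alone and the rate to be counted over both endpoints, and the top of the range also requires an assumed share of unmatched placebo periods. Equally, the text does not exclude separate fits. It does not tie the five subgroup statistics to the interaction model, nor say how five overlapping subgroups would enter as subgroup levels. For the interim route, the same section defines its statistics by the participants they cover, which can be read as separate fits.

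Three further points stand. The sextiles are inferred. Contributors could exceed 84, because the mITT rule keeps anyone with one post-baseline value on each endpoint. And 7.4.1 allows more participant data to be added if the covariance is poorly estimated. The first two leave the direction of the result unchanged. The effect of the third was not simulated.

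**Conclusion.** The point holds as a small defect with one unresolved ambiguity. The cut-offs ignore variance estimation, so the claimed one-sided 0.05 is exceeded under either reading. Under the interaction model the excess is about 0.004 to 0.006 per endpoint and 0.002 to 0.009 over both. Under separate fits with complete pairs it is about 0.014 to 0.015 per endpoint and 0.017 to 0.026 over both. The Hochberg rate is the relevant one for the Section 5 claim, because success on either endpoint counts.

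Severity is low if the interaction model is what is meant. Two analysts who both follow the text could nevertheless run primary tests with different true error rates, and that is reason enough to settle it. The point applies only to interventions without an interim that have a continuous primary biomarker. The documents do not say how many there will be. Cavosonstat, with a genotype biomarker and named in 7.4.1 as the example of dropping the biomarker-negative group after the interim, is not one of them. The figures rest on the assumptions listed with the inputs.

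**What to change.** Add two statements to SAP 7.4.1 before any unblinded analysis on this route:

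1. T^1 to T^5 come from the whole-sample MMRM with subgroup-by-treatment interaction and pooled variance, with one such fit for each cutoff.
2. Each of the six statistics is converted to a normal score through its t distribution, with Kenward–Roger degrees of freedom, before the maximum is taken and compared with 2.163 and 2.452.

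Stating the quantile levels of the five cutoffs would also let a reader verify the critical values.

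The cost is a sentence or two and a few lines of code. Power falls slightly, because the bar on the t scale rises. In the paired approximation, a converted score of 2.452 corresponds to a t of about 2.51 with 82 df. If subgroups were fitted separately, it would be about 2.83 for the subgroup of 14 (13 df).

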7.4.2 Intercurrent Events

The intercurrent events that could result in missing primary endpoint data (for FEV₁ and ACQ-6) include severe asthma exacerbations that interfere with the 16-week primary outcome assessment, major change in (biologic) therapy, and treatment or study discontinuation due to safety concerns (see Table 2). For the primary efficacy analysis, we will use two approaches to handle missing data depending on the reason for missingness:

1. Missing at random/other: primary endpoint values will be analyzed using the MMRM model described above. Non-informative reasons for missingness include major change in therapy due to change in insurance, availability of a new asthma treatment or due to an addition of a beta blocker; treatment discontinuation, study discontinuations, and loss-to-follow-up due to an administrative event or other event not related to treatment.
2. Informative: primary endpoint values will be handled by fitting the MMRM model described in Section 7.4.1. Informative reasons for missingness include worsening of asthma; major change in therapy due to worsening of asthma; and an adverse event that results in treatment discontinuation.

For intercurrent events that reflect a worsening of severe asthma (i.e., discontinuation due to exacerbations or side effects related to disease worsening), informative missingness (#2 above) will be assumed. For participants who discontinue a treatment period because of a major change in therapy, the reason for the therapy change will influence the approach for handling missing data. If a new asthma therapy becomes available, and the participant withdraws from the study to try the new therapy, the reason for missingness will be assumed to be non-informative (#1). If the reason for change in therapy is determined to be related to a decline in the participant's health status, informative censoring (#2) will be assumed. Treatment or study discontinuation due to adverse events or lab abnormalities will be assumed to be non-informative (#1).

In addition to the intercurrent events defined in Table 2, we anticipate some treatment discontinuations, study discontinuations, and loss-to-follow-up for other reasons that may result in missing primary endpoint data. Missing data resulting from these events will be assumed to be non-informative (#1).

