## 7 STUDY INTERVENTION DISCONTINUATION AND PARTICIPANT DISCONTINUATION/WITHDRAWAL

### 7.1 DISCONTINUATION OF STUDY INTERVENTION

#### 7.1.1 DISCONTINUATION OF A PARTICIPANT'S ASSIGNED INTERVENTION

Participants will be monitored for safety during the trial and the occurrence of certain adverse events or laboratory abnormalities will result in discontinuation from the participant's current treatment; that is, participation in the current treatment period will stop, and the participant will enter the washout period. The following adverse events or lab abnormalities will result in discontinuation from the participant's current treatment:

1. Serious infection (including pneumonia, cellulitis, kidney or neurologic infections, and any bacteremia/sepsis).
2. Any bleeding event thought to be associated with a platelet count reduction per the judgment of the center investigator.
3. Any other adverse event, per judgment of the center investigator, requiring discontinuation from treatment.
4. Laboratory values are monitored per the schedule of activities in Section 1.3. For adults, the below lab tests will be assessed at every 4-week visit during the treatment period. Abnormalities in the following laboratory values require prompt retesting within 3 to 5 days:
  - ANC <1000/ $\mu$ L for black participants, <1500/ $\mu$ L for other participants.
  - Lymphocyte count <500/mm^3.
  - Platelet count <50,000/mm^3.
  - Hemoglobin <9.0 g/dL.
  - AST and/or ALT elevation >3 times the upper limit of normal.
  - Bilirubin  $\geq$ 2 times the upper limit of normal.
  - Calculated eGFR < 54 mL/min/1.73 m^2 and baseline eGFR was >60 mL/min/1.73 m^2 OR calculated eGFR < 50 mL/min/1.73 m^2 and baseline eGFR was 54-60 mL/min/1.73 m^2

If both tests violate the following cut-off values, the participant is removed from treatment:

- a. Two sequential platelet counts <50,000/mm^3.
- b. One platelet count <25,000/mm^3 unless the confirmatory test demonstrates a count >50,000/mm^3. Treatment must be withheld pending the confirmatory retest.
- c. Two sequential neutrophil counts <500/mm^3.
- d. Two sequential lymphocyte counts <500/mm^3.
- e. Two sequential hemoglobin assessments <8.0 g/dL or >30% below the participant's initial baseline value or the baseline value for the current treatment period.

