### 9.2 SAMPLE SIZE DETERMINATION

An intervention is considered efficacious if significant benefit is shown for either of the two primary endpoints (FEV1% predicted, and ACQ-6). Because there are multiple chances for a test treatment to

demonstrate efficacy, multiplicity adjustments are required. We will use the Hochberg method to adjust for multiplicity.

A sample size of 111 participants is required to achieve 80% power to detect a treatment effect with respect to at least one of the two primary endpoints equal to 0.3 times the standard deviation (SD) of that endpoint, taking into account the possibility to stop for futility. The Type I error probability will be controlled under the global null hypothesis (no effect on either endpoint) at  $\alpha \leq 0.10$ . Power was estimated under the assumption of a within-participant, between-period correlation of responses on consecutive placebo and test treatment,  $\tau$ , of 0.70 and a treatment period discontinuation rate of 0.10. The required sample size for interventions with treatment period drop-out rates significantly different from 0.10, assessed based on pooled placebo and active treatment data, may be adjusted during the trial, prior to any unblinding. If futility analysis is not feasible for an intervention due to difficulty in participant accrual, 93 participants (2:1 ratio of biomarker positive to negative participants) are required to provide the same power described above.

Examples of treatment effects yielding a 0.3 standardized effect size include: a difference of 4.3 percent predicted FEV1 between intervention and placebo with a SD of 14.5 percent predicted; and a difference of 0.18 in average ACQ-6 symptom scores between the intervention and placebo with a SD of 0.6.

Given the experimental nature of the trial, the Type I error rate will be controlled at the two-sided 0.1 level. Our analysis method ensures a strong control of the Type I error rate at this level. Taking into account our stopping rule for futility, the Type I error rate is equal to about 0.05, two-sided, for  $\tau = 0.70$ .

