#### 9.5.2.1 MISSING DATA

We will use multiple imputation to handle missing data for the primary efficacy outcomes in a treatment period. Details of the planned imputation procedures and associated sensitivity analyses are provided in the Statistical Analysis Plan. Analysis of the Secondary Endpoint(s)

Secondary endpoints such as CompEx, FVC pre-BD, FEV1 post-BD, symptom free days (defined using diary/CompEx data) and asthma free days will be analyzed similar to the primary analysis model. Details of secondary analyses are provided in the Statistical Analysis Plan.

---

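### SAP 7.4.2 calls some missing primary data informative but analyses them with the same missing-at-random MMRM as the rest, so the effect may be biased if such dropout differs between active and placebo

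*SAP*

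**What the plan says.** SAP 7.4.2 sorts missing FEV₁ and ACQ-6 values into two classes by reason and announces an approach for each. Class 1 (missing at random and other) goes to the MMRM of SAP 7.4.1. Class 2 reads: "Informative: primary endpoint values will be handled by fitting the MMRM model described in Section 7.4.1". SAP 7.4.1 describes a single MMRM with no pattern-mixture, delta or reference-based component.

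The list of informative reasons ends with "major change in therapy due to worsening of asthma; and an adverse event that results in treatment discontinuation". The paragraph that follows says: "Treatment or study discontinuation due to adverse events or lab abnormalities will be assumed to be non-informative (#1").

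Protocol 9.5.2.1 states: "We will use multiple imputation to handle missing data for the primary efficacy outcomes in a treatment period". It refers to the SAP for the imputation procedures and the related sensitivity analyses. The SAP describes no imputation for these endpoints. SAP 7.4.3 has one sentence promising to examine sensitivity to the missing-data method, with no method, assumption or parameter. SAP Table 2 lists intercurrent events but gives no strategy for handling them.

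On data collection, Protocol 7.1.1 says that at discontinuation "participation in the current treatment period will stop, and the participant will enter the washout period". SAP 3.5.4 leaves out of the efficacy analyses anything measured after a major change in therapy.

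**The concern.** A likelihood MMRM is valid when missingness depends only on observed data. To label a class informative is to say that this condition fails for it. Sending that class to the unmodified MMRM contradicts the label, so the plan announces two approaches and delivers one.

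The values at issue are mostly lost by design, because discontinuation ends the treatment period. Where a participant stops because asthma worsened, any deterioration beyond what earlier visits predict is not seen by the model. If this happens more often on active than on placebo, the estimated benefit is too large. If it happens more often on placebo, the estimate is too small.

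This is the primary analysis of both primary endpoints for every intervention. As written, a statistician cannot tell whether to impute, what to do differently for class 2, or where adverse-event dropouts belong. Settling that after unblinding would leave room for a data-driven choice.

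**Working it through.** **Inputs from the documents.** Protocol 9.2: "Given the experimental nature of the trial, the Type I error rate will be controlled at the two-sided 0.1 level". SAP Section 5: "A sample size of 111 participants for each intervention is required to achieve at least 80% power to detect a treatment effect", with a target effect of 0.3 SD, a between-period correlation of 0.70, and about 10% discontinuing an active period soon after randomization. The SD is 14.5 points for FEV₁ percent predicted and 0.6 for ACQ-6. SAP 7.7.1: 34 biomarker-positive and 17 biomarker-negative participants at the interim, futility cutoff 1.29, and a null stopping probability of 0.74.

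**Step 1. The plan's own figures reproduce.**
- Futility under the null: with correlation √(2/3) between the positive-subgroup and combined statistics, P(max < 1.29) = 0.860 per endpoint. For two independent endpoints, 0.860² = 0.7396, against the stated 0.74.
- Power at 111: simulated with paired-difference variance 2(1 − 0.70) = 0.6 SD², 10% of pairs lost, and 0.3 SD in positives on one endpoint with no effect in negatives. The test used the inverse-normal combination with weights √0.45 and √0.55 and the Hochberg rule. Power is 0.82 to 0.83, consistent with at least 80%. Unmatched placebos were not modelled.

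This reproduction treats dropout only as lost pairs. It includes no shift in the mean.

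**Step 2. Analytic bias.** The documents give no dropout by arm or reason, so everything here is assumed. Let d_T and d_P be dropout on active and placebo, f the informative share, and g the unobserved deficit in SD beyond the missing-at-random prediction. Then

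bias = f × (d_T − d_P) × g.

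| d_T / d_P | f | g = 0.3 | g = 0.5 | g = 1.0 |
|---|---|---|---|---|
| 10% / 10% | any | 0 | 0 | 0 |
| 10% / 5% | 0.25 | 0.00375 | 0.00625 | 0.0125 |
| 10% / 5% | 1 | 0.015 | 0.025 | 0.05 |
| 15% / 5% | 0.25 | 0.0075 | 0.0125 | 0.025 |
| 15% / 5% | 1 | 0.03 | 0.05 | 0.10 |
| 5% / 15% | 0.25 to 1 | as for 15% / 5%, opposite sign | | |

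Relative to the target, 0.00375/0.30 = 1.25% and 0.10/0.30 = 33%. In outcome units, 0.05 SD is 0.05 × 14.5 = 0.7 FEV₁ points or 0.05 × 0.6 = 0.03 ACQ-6 units.

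**Step 3. Likelihood simulation.** Four visits in each of two periods, with dropouts losing the last two visits of the period; true effect 0.300 SD.

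| Dropout mechanism | Estimate (SD) |
|---|---|
| At random given observed visits, 10% in both | 0.297 |
| Not at random, 10% in both, same mechanism | 0.300 |
| Not at random 10% on active, purely random 10% on placebo | 0.324 (+8%) |
| Not at random, 15% active and 5% placebo | 0.335 (+12%) |

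Material bias appears only when not-at-random dropout differs between active and placebo.

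**Step 4. Scale against the standard error.** With 111 × 0.9 ≈ 100 pairs, SE = √(0.6/100) = 0.0775 SD. For one z-test at one-sided 0.025, a bias of 0.025 SD gives 1 − Φ(1.96 − 0.32) ≈ 0.05. A bias of 0.05 SD gives 1 − Φ(1.96 − 0.645) ≈ 0.09.

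**The case against.** The strongest reply is that the textual defects need not move the estimate, and much of it stands.

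- The MMRM uses each participant's own visits before dropout and, through the random intercept, other periods. Worsening recorded before stopping is therefore used; only the unrecorded excess matters.
- With one model for both classes, listing adverse events twice cannot change the current primary estimate. Ordinary missing-at-random imputation on the same variables would give about the same answer as the MMRM. These two points are inconsistencies, not sources of bias.
- The protocol limits such loss. Under 7.1.1, participants whose exacerbation responds to systemic steroids are not discontinued unless it is their third in the period. Under 7.2, poor compliers at no increased risk continue with assessments.
- The documented 10% covers discontinuation for any reason, soon after randomization. Participants with no post-baseline value are outside the mITT population (SAP 7.1), so neither the MMRM nor imputation of later visits reaches them.
- SAP 7.4.3 does commit to a missing-data sensitivity analysis. The gap is that it is unspecified, not that it is absent.

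None of this explains why a class labelled informative receives no method of its own.

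A reader might infer three stronger things that the documents do not support. The first is that the primary effect is biased: that requires differential informative dropout, and no rates by arm are given. The second is that the z-test figures in Step 4 are the trial's error rate. The plan uses a max-statistic combination test with Hochberg and a 0.74 null futility-stop probability, so they are only a gauge of scale. The third is that, if the 10% who stop active lose all benefit, 0.30 SD would be reported where 0.9 × 0.30 = 0.27 SD is true. That presumes an estimand that Table 2 does not state.

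**Conclusion.** The concern holds as a failure of the stated rule. SAP 7.4.2 gives its informative class the model that assumes it is not informative, places adverse-event discontinuation in both classes, and does not supply the multiple imputation that Protocol 9.5.2.1 says it contains. The unspecified promise in SAP 7.4.3 does not repair this.

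The primary effect may be biased, towards or away from the drug, if informative dropout differs between active and placebo periods. With dropout of 10%/5% or 15%/5% (or the reverse), an informative share of 0.25 to 1 and an unobserved deficit of 0.3 to 1.0 SD, the size is about 0.004 to 0.10 SD, or 1% to 33% of the 0.3 SD target. It is about zero if such dropout is alike in both. All these rates are assumptions. The textual findings are certain; the presence of bias is not established.

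**What to change.** 1. Keep the SAP 7.4.1 MMRM for class 1.
2. For class 2, replace the sentence with multiple imputation under a stated not-at-random assumption covering both active and placebo periods. One example is placebo-profile imputation for active-period dropouts plus a stated delta for informative dropouts in either period. Placebo-profile imputation alone would leave placebo-period dropouts at missing at random. Then fit the 7.4.1 model to each imputed data set and combine.
3. Put adverse-event discontinuation in one class only (class 2, as the list under approach 2 has it). Say in the same place where lab-abnormality discontinuation belongs, since it appears only in the later sentence, and delete that sentence.
4. Reconcile Protocol 9.5.2.1 with SAP 7.4.2.
5. In SAP 7.4.3, name the missing-at-random MMRM and a delta tipping-point analysis as the sensitivity analyses.
6. Have only the blinded statisticians make the change, as SAP 1.4 requires once unblinded review has begun. SAP 7.4.1 names cavosonstat as a case where the biomarker-negative subgroup was dropped, which indicates that its interim has taken place. For any intervention with an interim already analysed, keep the stage-1 p-values and the MMRM as primary, and make the not-at-random analysis the named sensitivity analysis.

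The cost is wording and programming, with no new data. The estimate may become slightly less favourable.
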